included in section 9.3 of protocol, but has now been added to the exclusion list for clarity.

-added language indicating that people with known hypersensitivity to lidocaine or epinephrine may not be able to participate as these agents are used for local anesthesia during skin biopsies.

Protocol Version 1.6  
May 01, 2017

Section 4.1: Clarified exclusion criteria as follows;

- Exclusion # 6 clarified to include “lung” transplant to match ICD

Section 5.2.3 and 6.2: Revised study drug titration schedule.

Section 9.3: Added language re: increased risk for fluid retention and edema to be consistent with risks for NSAIDs that are listed in the Salsalate package insert.

Protocol Version 1.7  
August 10, 2017

Section 3: Trial Design. Amended to reflect increased enrollment to 70 subjects and to modify randomization distribution from 1:1 (Salsalate:Placebo) to 3:2 (Salsalate:Placebo).

Section 5.1: Removed reference to 1:1 randomization ratio.

Throughout:

-Reference to enrollment of 60 subjects changed to 70 subjects

-Reference to salsalate dose clarified from “3 grams per day” to “up to 3 grams per day” to better reflect intent to use a lower dose for participants who experience dose-dependent, treatment related side effects.

-Clarified the randomization stratification by A1c from < 8% to >8% to ≤ 8.0% to >8.0%.

Protocol Version 1.8  
December 4th, 2017

Table 1: Amended to increase the allowable visit window between screening (visit 1) and baseline (visit 2)

Section 6.1: Amended last paragraph to reflect increase in allowable duration between screening (visit 1) and baseline (visit 2).

Throughout: Minor formatting changes and spelling/grammar corrections.

Protocol Version 1.9

July 11th, 2019

Section 2.0: Sudoscan removed from study procedures due to the bankruptcy of the manufacturing company and the subsequent inability to obtain supplies

Section 4.1: Clarified exclusion criteria as follows;

- Amputation Exclusion - edited exclusion criteria to allow patients who have had a lower limb amputation from a cause other than neuropathy
- Cancer Exclusion - edited exclusion criteria to only exclude patients with active cancer (other than basal cell or squamous cell skin cancer) rather than also excluding those who have had it in the last five years.
- Macroalbuminuria Exclusion - clarify that a history of persistent macroalbuminuria is checked by random urine microalbumin creatinine ratio rather than a 24-hour test.

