#### **4. STUDY POPULATION**

70 subjects with type 1 diabetes mellitus (T1DM) will be enrolled in this study.

This clinical trial can fulfill its objectives only if appropriate subjects are enrolled. The following eligibility criteria are designed to select subjects for whom protocol treatment is considered appropriate. All relevant medical and non-medical conditions should be taken into consideration when deciding whether this protocol is suitable for a particular subject.

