##### Exclusion Criteria

1. history of severe DN, active lower limb ulceration or lower limb amputation directly caused by diabetic neuropathy, or risk factors for any other causes of neuropathy (e.g. active hepatitis C, end stage renal disease, systemic lupus erythematosus or a known hereditary neuropathy) as determined through medical history, family history, history of medications, occupational history, history of exposure to toxins, physical and neurological examinations);

2. history of recent severe hypoglycemia (within prior 6 months) as defined by hypoglycemia resulting in coma or seizure or a history of recurrent diabetic ketoacidosis (DKA) or any diabetic ketoacidosis within the last three months.
3. history of persistent macroalbuminuria [random urine microalbumin creatinine ratio (ACR) >300 mg/gm]. ACR up to 300 mg/gm is acceptable if serum creatinine is <1.4 for women, <1.5 for men AND estimated GFR (eGFR) is > 60;
4. serum creatinine >1.4 for women and >1.5 for men or eGFR <60 [possible chronic kidney disease stage 3 or greater calculated using the Modification of Diet in Renal Disease (MDRD) equation];
5. pregnancy or lactation, or intention to become pregnant in next 12 months;
6. history of previous lung, kidney, pancreas, liver, cardiac or bone marrow transplant;
7. history of drug or alcohol abuse within the previous 5 years, or current weekly alcohol consumption >10 units/week;
8. use of warfarin (Coumadin), clopidogrel (Plavix), dipyridamole (Persantine), heparin or other anticoagulants, probenecid (Benemid, Probalan), sulfinpyrazone (Anturane) or other uricosuric agents; Subjects must agree to not use high-dose aspirin during the course of the study. Daily low-dose aspirin treatment (not more than 81 mg per day) may be continued if currently prescribed.
9. requiring long-term glucocorticoid therapy or chronic immunosuppressive therapy; Inhaled steroid use for management of asthma is not an absolute exclusion.
10. use of lithium
11. participation in an experimental medication trial within 3 months of starting the study;
12. current therapy for malignant disease other than basal- cell or squamous-cell skin cancer;
13. history of gastrointestinal bleeding or active gastric ulcer; screening laboratory abnormalities including AST (SGOT) and or ALT (SGPT) > 2.5 x the upper limit of normal (ULN), total bilirubin > 1.5 x ULN, platelets < 100,000;

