### **6.1. Recruitment/Screening**

#### Visit 1: Screening/Eligibility

An eligibility visit will be scheduled for subjects who, based on preliminary screening (telephone, email, medical chart review) meet the general entry criteria (age, T1DM, diabetes duration, symptomatic peripheral neuropathy, no contraindications for salsalate, etc.). At visit 1 the investigator or her designee will obtain written informed consent, after which all required eligibility examinations will be performed. The eligibility examination will include the following laboratory assessments: HbA1c, metabolic comprehensive panel (METCOMP), complete blood count with platelets (CBCP), thyroid stimulating hormone (TSH), lipid profile, cystatin-C, uric acid, urine albumin assessment, and in all women of child bearing age and potential, a urine

pregnancy test, even if an accepted method of contraception is being used. If any of the required laboratory measures are documented in the subject's medical record as being completed in the prior 3 months (1 month for HbA1c, and 6 months for urine albumin), they will not need to be repeated at the screening visit. Additional blood and urine will be obtained for Luminex assays of inflammatory markers. The Luminex assays though may be postponed until the baseline examination.

Weight, height and seated blood pressure and pulse will be obtained.

A structured neurologic history and physical examination and nerve conduction studies will be performed at the screening visit to verify and document the presence of signs or symptoms of peripheral neuropathy, the presence of a sural nerve response, and abnormality of at least one abnormal nerve attribute (amplitude, latency, conduction velocity or f-wave) in the sural, peroneal or ulnar nerve. In the absence of a sural nerve response (e.g., sural amplitude is 0  $\mu$ V, response is unobtainable, then the presence of a peroneal motor nerve conduction velocity of  $\geq$  35 meters per second will be required for inclusion. Quantitative sensory testing will also be conducted at the screening visit.

All visit 1 measures are ideally to be completed within a 4-week time frame but may take up to 6 months (180 days) if repeated measures are needed, and may be done at one, or over several visits if that is more convenient for the subject.

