### **9.3. Risks Associated with Study Medication**

The study is a randomized, double blind study and so neither the subject nor the study staff will know whether the medication is salsalate or a placebo. Not knowing what the actual study medication is may cause anxiety. Subjects who are not willing to accept random treatment assignment will not be accepted into the study.

The Belmar Research Pharmacy will maintain a master list of treatment assignments and in the event of a medical emergency, may be contacted to “unmask” the subject treatment.

Once the study is completed in all subjects, subjects may request their treatment assignment.

The common side effects of salsalate are nausea, loss of appetite, heartburn and feeling of ringing in the ears and some degree of deafness. These effects usually subside with ongoing treatment but if they persist, the dose of salsalate may be reduced. Subjects will be instructed to take the medication at mealtimes to reduce the GI side effects of the medication. While the GI and otologic side effects of salsalate tend to subside, if they persist or are troubling, the dose of salsalate may be reduced or salsalate may be stopped.

Salsalate may cause allergic reactions. People with known allergy to salsalate, aspirin, or to other NSAIDS are excluded from participating in the study. Subjects will be reported to stop salsalate treatment should they develop a rash, itching, hives, or difficulty breathing and to contact the study team or their usual health care provider right away. Emergency care may be required if the subject has breathing difficulties.

Salsalate and other salicylate medications in high doses can cause gastrointestinal bleeding, especially in patients with previous history of gastric ulcers. Patients with a history of GI bleeding or gastric ulcers are excluded from participation. Subjects will be advised of the risk for GI bleeding and provided information regarding signs and symptoms of GI bleeding and are asked to report these symptoms to the study team or to their regular health care provider.

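### Section 9.3 says patients with past gastric ulcers are excluded, but exclusion 13 bars only an active ulcer, so a healed ulcer that never bled is eligible under section 4.1

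*Combined protocol and SAP*

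**What the plan says.** Section 9.3 (Risks Associated with Study Medication) warns that salicylates in high doses can cause gastrointestinal bleeding, "especially in patients with previous history of gastric ulcers". It then gives the protection: "Patients with a history of GI bleeding or gastric ulcers are excluded from participation".

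The operative list is in section 4.1. Exclusion 13 reads "history of gastrointestinal bleeding or active gastric ulcer" and continues with laboratory limits.

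Two general provisions also bear on the point. Section 4 tells investigators: "All relevant medical and non-medical conditions should be taken into consideration when deciding whether this protocol is suitable for a particular subject". The telephone and chart pre-screen in section 6.1 lists entry conditions that include "symptomatic peripheral neuropathy, no contraindications for salsalate, etc". Neither mentions ulcer history.

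On concomitant treatment, exclusion 8 says: "Daily low-dose aspirin treatment (not more than 81 mg per day) may be continued if currently prescribed".

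**The concern.** The protocol names a risk group, says that group is kept out, and then uses a criterion that keeps out only part of it. Staff screen against the numbered list, and there the word *active* decides the outcome. Anyone who relies on section 9.3 to judge the trial's risk would believe in a safeguard that the list does not contain.

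At stake is the safety of a few individuals. A patient from the group singled out in section 9.3 could be given the study drug for a year. If already prescribed low-dose aspirin, that patient could keep taking it, and so take a second salicylate. The estimate of the treatment effect is not at issue.

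**Working it through.** **Step 1: apply both texts to each kind of patient.**

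| Patient | Exclusion 13 (section 4.1) | Section 9.3 |
|---|---|---|
| Any past gastrointestinal bleed | Excluded | Excluded |
| Active gastric ulcer | Excluded | Excluded |
| Healed gastric ulcer that bled | Excluded (bleeding history) | Excluded |
| Healed gastric ulcer, never bled | **Not excluded** | **Excluded** |

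The conflict is confined to the last row.

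**Step 2: see whether a softer reading removes it.** If the opening words of exclusion 13 were taken to reach past ulcers as well, *active* would do no work. If section 9.3 were taken to mean current ulcers only, the exclusion would not answer the risk in the sentence just before it, which concerns earlier ulcers. Neither is the natural reading.

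**Step 3: look for another rule that closes the gap.** The suitability clause in section 4 and the pre-screen in section 6.1 allow an investigator to decline the patient but do not require it. Exclusion 15 is about the likelihood of completing 12 months, not bleeding. The Summary of Changes records no edit to the ulcer criterion, so neither text is superseded.

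**Step 4: exposure.** Tablets are 500 mg (section 5.2.1) and the maximum is 2 tablets three times daily (section 5.2.3): 6 × 500 mg = 3,000 mg/day, for 12 months. Full dose may start from day 31. Table 1 schedules on-treatment laboratory tests, including blood counts, at months 3, 6, 9 and 12, and none at month 1. The first scheduled count can therefore come about two months into full dosing.

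**Step 5: size.** The documents give no prevalence of healed, never-bled gastric ulcer, so a prevalence *p* among enrolled subjects has to be assumed; 0.5% to 5% is used here. The planned total is 70. Allocation was 1:1 at first and 3:2 after August 2017 (section 3), so the number on salsalate lies between 70 × 1/2 = 35 and 70 × 3/5 = 42.

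- Expected number enrolled = 70*p*
- Expected number on salsalate = 35*p* to 42*p*
- Chance of enrolling at least one = 1 − (1 − *p*)^70

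| Assumed *p* | Enrolled | On salsalate | Chance of at least one |
|---|---|---|---|
| 0.5% | 0.35 | 0.18 to 0.21 | 0.296 |
| 1% | 0.70 | 0.35 to 0.42 | 0.505 |
| 5% | 3.5 | 1.75 to 2.1 | 0.972 |

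**The case against.** The strongest reply is that section 9.3 is current text of the same protocol and states the exclusion outright. Nothing says section 4.1 overrides it, so the patient is eligible only if the list is read alone. The version 1.5 change can be read the same way. Hypersensitivity wording was described as "included in section 9.3 of protocol, but has now been added to the exclusion list for clarity", which suggests the sponsor regarded the section 9.3 exclusion as already in force. On this view the mismatch is a matter of tidying.

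Further, the prevalence range has no support in the documents, spans a factor of ten, and counts enrolments rather than bleeds. It makes no allowance for the pre-screen, the suitability judgement or the medical history taken at screening and baseline. The current version dates from September 2022, so an amendment can protect only subjects not yet enrolled, and their number is not given. Continuing aspirin was a deliberate choice that applies to everyone. Safeguards are substantial: anticoagulants, clopidogrel and platelets below 100,000 are excluded, dosing is titrated and taken with meals, subjects are counselled about bleeding, tolerance is checked at one week and one month, and the DSMB meets every three months.

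Much of this stands as a limit on size. The prevalence figures are illustrative, no bleeding risk has been estimated, and investigators may well be declining such patients already. But these points do not remove the conflict. Section 9.3 describes a categorical exclusion, and discretion and monitoring are not equivalent to one. Eligible here means not barred by the numbered criteria, which is how eligibility is checked in practice. The version 1.5 precedent also shows that the sponsor has thought it worth carrying a section 9.3 exclusion into the list.

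**Conclusion.** The concern holds. For a healed gastric ulcer that never bled, two current sections give opposite answers, and the one used for screening is the less protective. Confidence in the textual conflict is high, since it rests only on the wording.

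The practical size is small and uncertain: probably somewhere between no subjects and a handful, on an assumed prevalence, with no figure available for resulting harm. The correction should be made because it restores a safety exclusion the protocol already claims, at almost no cost.

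**What to change.** Amend exclusion 13 so that its ulcer clause covers any gastric ulcer, active or past, and leave the bleeding-history clause and laboratory limits unchanged. The list would then match section 9.3.

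If the investigators deliberately wish to admit healed ulcers, amend section 9.3 instead to say that only active gastric ulcers are excluded, so that the stated protection is accurate. One of the two texts has to change.

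The preferred change is a one-line amendment and needs no new procedure. It would lose about 0 to 4 otherwise eligible patients per 70 under the assumed 0.5% to 5% range (70 × 0.005 = 0.35; 70 × 0.05 = 3.5), and it acts only on subjects not yet randomized.

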#### **9.4. Risks Associated with Nerve Conduction Studies**

Risks associated with nerve conduction studies are the discomfort associated with these studies. The subjects will be alerted that they will feel a sensation similar to a “carpet shock” or snap from a rubber band during the test and will be reassured that the sensation will be temporary. A skilled electromyographer will perform the studies and care will be taken to minimize the discomfort associated with the studies.

#### **9.5. Risks Associated with Skin Biopsies**

The risks associated with skin biopsies are pain, bleeding, bruising, or infection. Subjects may be left with a small scar or discolored area at each biopsy site. Four sites are biopsied in the course of the study, each about 3 mm in diameter. The skin biopsies will be done by members of the staff who have training and experience in doing them. The areas biopsied will be cleaned with antiseptics prior to the biopsy and a local anesthetic used to reduce pain. Subjects will be given written information about wound care and how and when to report any signs or symptoms of infection. The study staff will call the subject within one week each biopsy to check on how it is healing.

#### **9.6. Risk Associated with Cardiovascular Autonomic Testing**

Participants will be asked to fast in preparation for testing and are therefore at heightened risk for hypoglycemia. The study team will advise the subject regarding adjustments to insulin dosing to reduce the risk for hypoglycemia. Testing will be scheduled in the morning to shorten the duration of fasting. The test itself has few risks associated with it, although some patients may become dizzy or lightheaded when moving from supine to standing, or after performing valsalva maneuvers. Subjects will be reminded to report any dizziness or lightheadedness immediately to the examiner and will be instructed to return to a seated or lying position as needed to relieve symptoms.

### **10. DATA ANALYSIS/STATISTICAL METHODS**

Detailed methodology for summary and statistical analyses of the data collected in this trial will be documented in a Statistical Analysis Plan, which will be prepared during the R34 and finalized prior to breaking of the blind.

#### **10.1. Sample Size Determination**

The purpose of this clinical trial is to provide the preliminary data necessary to design a larger

multi-site clinical trial. There are two assumptions that are necessary to justify the larger trial. The first is that salsalate will cause an increase in nerve fiber density (re-innervation) and the second is that the natural progression of DN, even with treatment for diabetes, leads to loss of nerve fibers. The primary outcome is an assessment of IENFD at the distal thigh after 12 months of placebo or salsalate treatment.

In the largest study of IENFD, Lauria et al provided a table of median IEFND values in the distal leg as a function of age and gender. In the 20-29 age range the average IEFND was 12.2 fibers/mm with an average decline of 0.1 fibers/mm per year. We reported that the average IEFND in the distal leg in T1DM subjects (mean disease duration of 27 years) was 2.2 fibers/mm. If we assume that our diabetic subjects have the average IENFD for ages 20-29 shown by Lauria et al at the start of their disease, then the decline due to diabetes was 10 fibers/mm or an average of 0.25 fibers/mm /year. If the decline is more rapid as neuropathy progresses, then the average decline in IEFND may be as high as 0.5 fibers/mm/year.

In a study of the effect of physical exercise Smith et al found an increase in the IENFD at the thigh of 1.4 fibers/mm after one year of intervention. Based on our assumption about the mechanism by which salsalate will influence IEFND (reduction of inflammation), we believe that a similar increase in fiber density is possible with treatment with salsalate. In multiple studies that reported a change in IEFND over time (including one of our own studies), the standard deviation of the change was approximately 2 fibers/mm. With the above assumptions, there will be an expected difference of 1.65 fibers/mm ( $0.25 + 1.4 = 1.65$ ) in the change between the two groups at the thigh with a standard deviation of 2.0. With 25 subjects per group there will be 81% power to reject the null hypothesis of no difference between groups using a two-tailed t-test at a 5% level of significance. Prior data are insufficient to perform a power calculation for the distal leg.

The trial will be considered a success if the primary endpoint demonstrates a significant difference between the two groups and one other secondary endpoint trends in a similar direction. This trial will also be considered a success if there is sufficient evidence to show that IEFND increases with salsalate but is likely to decrease with usual treatment. With 25 subjects per group, the standard error of the estimate will be approximately 0.4 [=2/square root (25)] and therefore the confidence interval for the mean change in each group will be the estimated mean change  $\pm$  0.8 fibers/mm; i.e. an increase of greater than 0.8 fibers/mm with salsalate and an observed decrease with placebo (since the expected decrease with placebo is not expected to be large). With these results, this trial would provide the preliminary data needed for a larger trial to validate the effect of salsalate. Assuming 15-20% attrition rates, 70 subjects will be recruited to attain the necessary 50.

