### 1.2. Rationale

Evidence for an important role of low-grade inflammation and of nuclear factor kappa B (NF- $\kappa$ B) activation in the pathogenesis of DN and in the pain syndrome associated with DN is emerging from both experimental  and clinical studies . This suggests that agents with known anti-inflammatory properties, such as salicylates, may prevent the development of DN and the pain associated with DN. Salsalate, a pro-drug form of salicylate, is indicated for relief of the signs and symptoms of rheumatoid arthritis, osteoarthritis and related rheumatic disorder. It is a highly effective drug in blocking the IKK $\beta$ /NF- $\kappa$ B pathway, and can be obtained at a low cost. Salsalate has recently been shown to have glucose lowering effects.

The recently published NIDDK-funded “Targeting Inflammation Using Salsalate in Type 2 Diabetes (TINSAL-T2D)” trial confirmed salutary effects of 3.5 gram/day salsalate on markers of inflammation, glucose control and overall safety after 48 weeks in patients with type 2 diabetes (T2DM).

Our initial NIDDK funded R03 (DK 094499) grant confirmed the safety and feasibility of targeting inflammation with salsalate treatment in T1DM subjects with DN (26). Our current study builds upon and expands our initial promising results and will either confirm or refute the therapeutic efficacy of salsalate in a larger T1DM cohort.

Traditionally the diagnosis of DN is made by the presence of abnormal nerve conductions (NC), and a combination of symptoms and signs of distal sensorimotor polyneuropathy. However, NC studies assess only large myelinated nerve fiber function and in early DN, these conventional measures can be normal and if abnormal, change slowly. Recent data have also described minimal worsening  or improvement in NC  in placebo and epidemiological cohorts with little relation to other measures of small fiber nerve function in diabetic patients. This was further confirmed by the relative modest changes in all NC studies in the DCCT/EDIC cohort during 13-14 years of follow-up while adhering to current standard of care .

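### Section 10.1 lets success be declared on within-arm changes alone, and it pairs the new recruitment figure of 70 with attrition, completer, group-size and power figures from the 1:1 design

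*Combined protocol and SAP*

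**What the plan says.** Section 10.1 (Sample Size Determination) gives two routes to success.

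- **Route 1:** a significant difference between groups on the primary endpoint, plus one secondary endpoint trending the same way.
- **Route 2:** "This trial will also be considered a success if there is sufficient evidence to show that IEFND increases with salsalate", together with a likely decrease under usual treatment. The section puts this in numbers as "an increase of greater than 0.8 fibers/mm with salsalate and an observed decrease with placebo".

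The setting is a planning one. The section opens by saying that the trial is to supply preliminary data for a larger one, and adds "There are two assumptions that are necessary to justify the larger trial". After the numerical rule it says "With these results, this trial would provide the preliminary data needed for a larger trial to validate the effect of salsalate". Section 1.2, however, says that the study "will either confirm or refute the therapeutic efficacy of salsalate in a larger T1DM cohort", and Section 3 labels the trial phase II-III. Section 10.2 specifies the primary analysis as a between-group linear model for change in IENFD, adjusted for HbA1c stratum and baseline IENFD.

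On size, Section 3 records a change from up to 60 subjects at 1:1 to up to 70, with those enrolled after approval of the revision randomised 3:2. One reason given is differential discontinuation of study medication. Section 10.1 states "With 25 subjects per group there will be 81% power to reject the null hypothesis of no difference between groups" (repeated in the synopsis), "With 25 subjects per group, the standard error of the estimate will be approximately 0.4", and "Assuming 15-20% attrition rates, 70 subjects will be recruited to attain the necessary 50".

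**The concern.** Route 2 is introduced as an additional, sufficient route. It compares each arm with its own baseline, asks only for a negative point estimate on placebo, and drops route 1's secondary-endpoint condition. The trial could therefore be called a success in the protocol's own terms while its randomised comparison is not significant.

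The planning figures also do not fit together. The recruitment number is now 70, but the attrition range, the 50 completers, the 25 per group, the common standard error and the 81% power stayed as they were. A reader cannot tell from Section 10.1 how many completers, how much power or what precision the current design is expected to give.

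**Working it through.** **Inputs.** From Section 10.1: difference 1.65 (+1.4 on salsalate, -0.25 on placebo), SD of change 2.0, two-sided 5% t-test, 25 per group, attrition 15-20%. From Section 3: 60 at 1:1, then up to 70 with later enrolees at 3:2. The number already randomised 1:1 (k) is not given, so k = 0 to 60 is assumed. A two-sample t-test stands in for the Section 10.2 model, route 1's secondary condition is taken as met, and completers are the unit of information.

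**The plan's own figure.** Noncentral t, 25/25: power = 81.5%. The stated 81% reproduces.

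**Route 2 without significance.** Take +0.85 on salsalate and -0.05 on placebo, a gap of 0.90. At 25/25, SE = 2 × sqrt(2/25) = 0.566, t = 0.90/0.566 = 1.59, p = 0.118. Over 25/25, 30/20, 34/22, 36/24, 29/27 and 31/29, p runs from 0.087 to 0.126, and significance needs a gap of 1.03 to 1.16. If the covariates explained 20% of the variance (assumed), p would be 0.056-0.088; at 40% (assumed) the example would be significant.

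**How often it matters.** Route 2 alone has probability P(salsalate mean > 0.8) × P(placebo mean < 0). At 25/25 with no change in either arm this is 0.0228 × 0.5 = 1.1%. The either-route figures come from simulation (4,000,000 draws per case). Ranges cover the six allocations.

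| True mean change | Route 1 alone | Either route | Route 2 alone |
|---|---|---|---|
| Both -0.25 (the plan's untreated decline) | 2.5% | 2.5-2.6% | 0.06-0.32% |
| Both 0 | 2.5% | 2.6-2.9% | 0.4-1.1% |
| Both +0.4 (assumed shared improvement) | 2.5% | 3.1-3.6% | 1.9-2.5% |
| +1.4 vs -0.25 (planned effect) | 80-88% | 83-89% | 68-71% |

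If both arms change by -0.25, 18-30% of route-2 successes lack a significant comparison. Because route 2 itself occurs in at most 0.32% of such trials, that is under 0.1 percentage point. At the planned effect the share is 2-4%.

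**Attrition sentence.**
- 70 × 0.85 = 59.5 and 70 × 0.80 = 56, so 56-60 completers.
- 1 - 50/70 = 28.6% attrition would be needed to end with 50.
- 50/0.85 = 59 and 50/0.80 = 63 recruits (rounded up) would be needed for 50 completers.
- 60 × 0.85 = 51 and 60 × 0.80 = 48, so the attrition range and the 50 fit the former 60.

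**Completers, power and precision now.** With k at 1:1 and the rest at 3:2, randomised numbers are salsalate 42 - 0.1k and placebo 28 + 0.1k. The half-width is 1.96 × 2/sqrt(n).

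| Case | Salsalate / placebo completers | Power | Half-widths |
|---|---|---|---|
| Stated | 25 / 25 | 81.5% | 0.78 both |
| k=0, 15% | 35.7 / 23.8 | 86.5% | 0.66 / 0.80 |
| k=0, 20% | 33.6 / 22.4 | 84.4% | 0.68 / 0.83 |
| k=60, 15% | 30.6 / 28.9 | 87.8% | 0.71 / 0.73 |
| k=60, 20% | 28.8 / 27.2 | 85.8% | 0.73 / 0.75 |
| 50 complete, k=0 | 30 / 20 | 80.0% | 0.72 / 0.88 |
| k=0, assumed 40% salsalate and 20% placebo attrition | 25.2 / 22.4 | 79.4% | 0.78 / 0.83 |

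**The case against.** The strongest defence of route 2 is its context. Section 10.1 opens with the larger trial, names two premises that would justify it (density rises on salsalate, falls without it), and route 2 matches them one for one. The text leaves validation to the later trial. Nothing says that route 2 replaces the Section 10.2 analysis, and the line in Section 1.2 is rationale, not a decision rule. Most of this stands, and it makes the problem one of labelling. It does not remove the problem, because the same word, success, covers both routes without qualification.

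Route 2 alone is also harder to meet than the primary test in nearly all the cases above, and the +0.85/-0.05 example sits just past both cut-offs under an unadjusted test. That stands too. A reader might infer serious inflation of false success; the table does not support that. The 3.1-3.6% figures need a shared improvement that runs against the plan's own expectation of decline.

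On the numbers, 50 could be read as a minimum that 56-60 satisfies. But the sentence presents 70 as the result of applying 15-20% attrition to reach 50, and it is not. Nor was the 70 itself left behind; what stayed is the attrition range and the 50 beside it, with the equal groups of 25 and what was computed from them.

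**Conclusion.** Both parts hold, with modest impact. Route 2 permits a declaration of success without a between-arm test, which adds at most about 0.4 percentage points to one-direction false success if the arms both change by 0 or by -0.25. The planned Section 10.2 analysis is not affected.

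The planning figures in Section 10.1 are mutually inconsistent and do not describe the current allocation. Two opposite inferences are tempting, and the documents support neither. One is that the trial is underpowered: at equal attrition of 15-20%, power is about 84-88%, above the stated 81%. The other is that power is therefore assured: Section 3 cites differential discontinuation of medication without rates. Stopping medication is not the same as missing the month-12 biopsy, but if completion differed in the same way, power could be at or slightly below 80%.

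All this rests on SD 2, a t-test in place of the covariate-adjusted model, and an unknown number already randomised 1:1.

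**What to change.** In Section 10.1, and for the power statement in the synopsis:

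1. Make the Section 10.2 between-arm comparison, with the existing secondary-endpoint condition, the only basis for declaring success. Relabel the other rule, for example: A mean increase above 0.8 fibers/mm with salsalate and an observed decrease with placebo will be reported descriptively, with within-group confidence intervals, as support for planning the larger trial.
2. Reconcile the attrition sentence: either 70 recruited with 56-60 expected to complete at 15-20%, or state the attrition that yields 50 (28.6%).
3. Restate expected completers, power and confidence-interval half-widths by arm, using the actual number already randomised 1:1 and the attrition expected in each arm.

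Sample size, data collection and analysis stay as they are. Section 10 says that the detailed analysis plan is finalised before the blind is broken, so the same wording can go there. The cost is about 1.3 to 3.0 percentage points of nominal success probability at the planned effect (for example 84.5% to 81.6% at 25/25).
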